1.3 Secondary Study Endpoints

State the secondary endpoints to be measured in the study.

- Conditional Weight Gain during the intervention period spanning Ages 1-6 Months
- Mean Weight-for-Length Z-score (WLZ) at Age 6 Months
- Growth Trajectory during the intervention period spanning Ages 1-6 Months (repeated measures of weight-for-length)
- Proportion of Infants with Overweight (Weight-for-Length $\geq 95^{\text{th}}$ Percentile on WHO Growth Charts) at Age 6 months
- Feasibility: a) recruitment, b) ability to give tailored formula volume recommendations, c) visit completion, d) retention through 6 months
- Acceptability: parent adherence to formula volume recommendations as measured by 3 day feeding diaries at 2, 3, 4, 5, and 6 months for the intervention group

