3.1 Inclusion Criteria

Create a numbered list of the inclusion criteria that define who will be included in your final study sample (e.g., age, gender, condition, etc.)

1. Term or Early Term (≥ 37 weeks), singleton infants
2. Infant birthweight $\geq 50^{\text{th}}$ percentile based on the 2013 Fenton Growth Charts (which account for sex of child and gestational age at birth)
3. Infant without substantial neonatal morbidity that would affect feeding or weight gain (e.g. known chromosomal abnormality, metabolic disorder, cleft lip/palate, etc.)
4. Infant age ≤ 1 month
5. Mothers with pre-pregnancy body mass index $\geq 25 \text{ kg/m}^2$
6. Mothers ≥ 18 years old
7. Parental plan to exclusively feed infant 19-20 kcal/ounce formula upon delivery or by the start of the intervention period ~ 1 month after delivery
8. Parental intention to have infant well child visits through age 6 months at a Division of Academic General Pediatrics practice site (Hope Drive, Elizabethtown, Nyes Road)
9. English speaking parent

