7.1 Study Design

Describe and explain the study design.

This study is a randomized, clinical trial involving 60 exclusively formula fed infants born at ≥ 37 weeks gestational age who are at-risk for overweight based upon maternal pre-pregnancy overweight or obesity (or alternatively at first prenatal visit if pre-pregnancy weight/height not known) and infant birthweight $\geq 50^{\text{th}}$ percentile. Infants will be enrolled at Penn State Health Children's Hospital or at affiliated clinics within the Division of Academic General Pediatrics between birth and age 1 month, where they will be randomized to a calibrated formula intake intervention or control. Participating infants in the intervention group will be seen monthly until age 6 months where they will be weighed and measured, and parents will complete surveys related to volume of formula consumed, infant appetite, parent feeding style, and infant temperament. Control infants will follow the same procedures, but will not have scheduled visits at ages 3 and 5 months. Instead their visits will correspond to usual care well child visits at ages 1, 2, 4, and 6 months.

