- a) Volume consumed in each feeding for the day (volume is the amount that passes the infant's lips – if formula is spit-up, it still counts as having been consumed)
- b) Type of infant formula
- c) Size of bottle used
- d) Other sources of nutrition (e.g. juice, water, foods)

Randomization – following the visit, infants will be randomized to intervention or control using a computer-generated randomization program generated by a statistician not affiliated with the trial. Randomization will include stratification for sex of the infant (male/female) and maternal pre-pregnancy BMI category ($25-29.9 \text{ kg/m}^2$ vs. $\geq 30 \text{ kg/m}^2$).

7.2.2 Visit 2

Provide a description of what procedures will be performed on visit 2 or day 2 or post-test in order of how these will be done. If your study involves more than two sessions or visits replicate this section for each additional session or visit (e.g., 7.2.3, 7.2.4, etc.).

Age 1 Month Visit (ages 24 – 41 days)

Both study groups:

1. Anthropometrics of infant (weight, recumbent length)
2. Parent-completed Surveys
 - a. Baby Eating Behavior Questionnaire⁷⁶
 - b. Babies Basic Needs Questionnaire

- c. Single item adapted from the Infant Feeding Practices Study II⁷⁷: “I encourage my infant to finish his or her bottle of formula”⁷⁸; responses include:
Never Rarely Sometimes Most of the time Always.....
- 3. Diary cards to be completed for the 3 days following the visit
- 4. Diary cards to be completed x 3 days prior to next study visit

Intervention group only:

1. Parents will be provided with handouts on hunger/satiety cues and calming a fussy baby
2. Parents will be given a digital streaming copy of the video, “Happiest Baby on the Block” available at: <https://www.happiestbaby.com/products/baby-streaming-video-english>
3. Parents will be given a copy of a video demonstrating responsive bottle feeding: <https://youtu.be/NLnPGJKdPUw>⁷⁸
4. Parents will be given a copy of Bottle Feeding Basics video: <https://360.articulate.com/review/content/99a63b9a-184c-474e-b836-7d8cd8aa1652/review>
5. Study coordinators will provide parents with a range of formula volume to be consumed based upon research conducted by Butte:⁷⁹

Table 8 Energy requirements for formula-fed infants 0–12 months of age

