Age (months)	Weight (kg) ^a	Weight velocity (g day ⁻¹) ^b	Total energy expenditure (kJ day ⁻¹)	Total energy expenditure (kcal day ⁻¹)	Energy deposition (kJ day ⁻¹)	Energy deposition (kcal day ⁻¹)	Energy requirement (kJ day ⁻¹)	Energy requirement (kcal day ⁻¹)	Energy requirement (kJ kg ⁻¹ per day)	Energy requirement (kcal kg ⁻¹ per day)
Boys										
1	4.58	35.2	1462	349	884	211	2345	560	512	122
2	5.5	30.4	1779	425	764	183	2543	608	462	111
3	6.28	23.2	2049	490	582	139	2631	629	419	100
4	6.94	19.1	2277	544	224	53	2501	598	360	86
5	7.48	16.1	2464	589	189	45	2653	634	355	85
6	7.93	12.8	2619	626	150	36	2770	662	349	83
7	8.3	11.0	2747	657	69	17	2816	673	339	81
8	8.62	10.4	2858	683	65	16	2923	699	339	81
9	8.89	9.0	2951	705	57	14	3008	719	338	81
10	9.13	7.9	3034	725	89	21	3123	746	342	82
11	9.37	7.7	3117	745	87	21	3204	766	342	82
12	9.62	8.2	3203	766	93	22	3296	788	343	82
Girls										
1	4.35	28.3	1382	330	746	178	2128	509	489	117
2	5.14	25.5	1655	396	672	161	2327	556	453	108
3	5.82	21.2	1890	452	559	134	2449	585	421	101
4	6.41	18.4	2094	500	285	68	2379	569	371	89
5	6.92	15.5	2270	543	239	57	2510	600	363	87
6	7.35	12.8	2419	578	199	47	2617	626	356	85
7	7.71	11.0	2543	608	83	20	2626	628	341	81
8	8.03	9.2	2654	634	69	17	2723	651	339	81
9	8.31	8.4	2751	657	63	15	2814	673	339	81
10	8.55	7.7	2834	677	74	18	2908	695	340	81
11	8.78	6.6	2913	696	63	15	2976	711	339	81
12	9	6.3	2989	714	60	14	3049	729	339	81

^a50th percentile weight for age of the WHO pooled breast-fed data set³⁶.

^b50th percentile weight increment of the WHO pooled breast-fed data set³⁶.

Recommended formula volumes will be calculated based on data from the table above informing parents of the recommended formula volume based on 19/20 kcal/ounce formula at the infant’s current age as well as the anticipated volume at the infant’s next visit as described below.

For those with weight-for-length (WFL) <75th percentile on the WHO WFL growth chart, recommended daily formula volumes will be calculated based upon the infant’s sex, current age, weight, and energy requirement (kcal/kg/day). Further, parents will be informed of the volume to expect at the subsequent visit in one month should the child maintain the same weight-for-age percentile.

For those with WFL ≥75th percentile on the WHO WFL growth chart, recommended daily formula volumes will be calculated based upon the child’s current age, weight, and energy requirement (kcal/kg/day) with a 10% reduction in daily volume. Further, parents will be

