8.3 Statistical methods

Describe the statistical methods (or non-statistical methods of analysis) that will be employed.

We will assess conditional weight gain from birth to 6 months to assess rapid infant growth.^{80,81} Conditional weight gain will be calculated as standardized residuals from the linear regression of weight for age at 6 months on weight for age at birth, with length for age at birth and 6 months and infant age at the 6-month visit entered as covariates. We will explore the moderating role of child sex, delivery mode, and maternal parity on intervention effects. Similar analyses will be conducted for the intervention period spanning ages 1-6 months.

For cross-sectional analyses at age 6 months, ANOVA will estimate the effects of intervention group on mean weight-for-length. Logistic regression will be used to compare intervention effects on the dichotomous outcome of overweight at 6 months.

For growth from 1-6 months, we will fit a repeated measures ANOVA of BMI, with visit and study group as within and between factors, respectively.

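### The 1-6 month growth model enters the pre-intervention 1-month value as an outcome and names no term as the test; a 1-month-adjusted 6-month contrast would be clearer and usually more powerful

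*Combined protocol and SAP*

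**What the plan says.** Section 1.3 lists as a secondary endpoint "Growth Trajectory during the intervention period spanning Ages 1-6 Months (repeated measures of weight-for-length"). Section 8.3 gives its analysis: "we will fit a repeated measures ANOVA of BMI, with visit and study group as within and between factors, respectively". That sentence mentions no covariate, no group-by-visit term, no contrast, no covariance structure and no sphericity correction. (It also models BMI where section 1.3 has weight-for-length. That is a separate matter and does not affect this point.)

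On timing:

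- Section 7.1 says that controls "will not have scheduled visits at ages 3 and 5 months", and continues: "Instead their visits will correspond to usual care well child visits at ages 1, 2, 4, and 6 months". The visits common to both arms are therefore 1, 2, 4 and 6 months.
- Section 3.1 places the feeding plan "by the start of the intervention period ~ 1 month after delivery".
- Section 7.2.2 lists the handouts, videos and first volume recommendation at Visit 2 (age 1 month), for the intervention group only; for example, "Parents will be provided with handouts on hunger/satiety cues and calming a fussy baby". The recommendation is computed from the infant's "current age, weight, and energy requirement (kcal/kg/day"), so the infant must be weighed before it is given.
- Section 7.2.1 places randomization after Visit 1.

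The 1-month value is thus taken after randomization but before any intervention component is delivered.

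**The concern.** A between-group effect averaged over all visits includes one visit at which the expected difference is zero, so it understates the effect of the intervention. The model also leaves unused the best available predictor of later size, the infant's own 1-month value. Because no test is named, two analysts following section 8.3 could report different terms that answer different questions and have very different power.

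Section 8.2 says the pilot data will be used to size a full trial. If a group effect understated by a quarter were used as the planning effect, the required sample would rise by (1/0.75)² = 1.78, other things equal.

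**Working it through.** The documents give no SD, correlation, effect size, alpha or power for this endpoint, so there is no figure of the plan's own to reproduce.

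**Inputs from the documents.** Common visits at 1, 2, 4 and 6 months (7.1); analysis span 1-6 months (8.3); intervention starting at the 1-month visit (3.1, 7.2.2); 60 infants (8.1).

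**Assumed.** 30 per arm (the allocation ratio is not stated); SD 1; two-sided 5% level; correlation ρ^(months apart) with ρ = 0.80, 0.85, 0.90; group differences of 0, 0.12, 0.36 and 0.60 SD at 1, 2, 4 and 6 months.

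**1. Group main effect.** With four equally weighted visits and no effect at 1 month, it is (0 + d2 + d4 + d6)/4 = 3/4 × (d2 + d4 + d6)/3. The factor does not depend on the shape of the effect:

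- constant (0, 1, 1, 1): 0.75 against 1.00
- linear (0, 0.2, 0.6, 1): 0.45 against 0.60
- late (0, 0, 0.5, 1): 0.375 against 0.50

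In the assumed scenario it is 1.08/4 = 0.27 against 1.08/3 = 0.36. Six visits would give 5/6, but controls have no 3- or 5-month visit.

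**2. Interaction.** This tests whether the four visit-specific differences are equal, with (2 − 1)(4 − 1) = 3 df. The zero at 1 month is the reference from which the arms diverge, so it does not dilute this test.

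**3. Illustrative power (6,000 simulated trials per column).**

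| Test | ρ = 0.80 | 0.85 | 0.90 |
|---|---|---|---|
| Group main effect, four visits | 24% | 22% | 20% |
| Same, 1-month level dropped, no adjustment | 37% | 34% | 31% |
| Visit-by-group, Greenhouse-Geisser corrected | 47% | 55% | 70% |
| Mean of 2, 4, 6 months, adjusted for 1 month | 58% | 62% | 71% |
| 6-month difference, adjusted for 1 month | 67% | 72% | 80% |

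Repeat runs differ by about a point, hence 66-80% for the last row.

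Hand check of the first row: the variance of a four-visit mean is [4 + 2(ρ + 2ρ² + ρ³ + ρ⁴ + ρ⁵)]/16. This is 0.666 at ρ = 0.80 and 0.812 at 0.90. The standard errors are √(2/30 × 0.666) = 0.211 and √(2/30 × 0.812) = 0.233. Then 0.27/0.211 = 1.28 and 0.27/0.233 = 1.16, and with a critical value near 2.00 power is about 24% and 20%.

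Hand check of the last row: the residual variance is 1 − ρ¹⁰, which is 0.893 and 0.651. The standard errors are 0.244 and 0.208, the ratios 0.60/0.244 = 2.46 and 0.60/0.208 = 2.88, and power about 68% and 81%.

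**4. Type I error of the interaction.** Without a sphericity correction it rejected in 6.0-7.2% of null trials. The Monte Carlo standard error is about √(0.07 × 0.93/6000) = 0.3 points, so about 6-8%. With Greenhouse-Geisser correction it was 4.1-4.9%.

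**5. Change from 1 month as an alternative.** The 6-month change has variance 2(1 − ρ⁵). The adjusted 6-month value has (1 − ρ⁵)(1 + ρ⁵). The ratio 2/(1 + ρ⁵) is 2/1.328 = 1.51 at ρ = 0.80 and 2/1.590 = 1.26 at ρ = 0.90, so change is valid but less efficient.

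**6. Sensitivity to the assumed shape.** Take equal correlation between all visits and a constant effect of 0.6 SD. Interaction power is 65% at ρ = 0.5 and 97% at ρ = 0.8. The adjusted 6-month difference has standard error √(2/30 × (1 − ρ²)) = 0.224 and 0.155, ratios 2.68 and 3.87, and power about 75% and 97%. The advantage is then about 10 points at ρ = 0.5 and none at ρ = 0.8.

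**The case against.** The strongest reply is that section 8.3 never says the group main effect is the test. For an endpoint called a growth trajectory, the usual term in a visit-by-group ANOVA is the interaction, and the 1-month level belongs in it. This stands. A reader might infer that the planned effect is diluted by a quarter, or that the plan has 20-24% power where 66-80% was available. The documents support neither statement, because both presuppose a choice of term that the plan has not made.

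Further points on the same side:

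- Most of the gap between the main effect and the proposed contrast does not come from the 1-month level. Dropping that level alone raises power only to 31-37%; the rest comes from covariate adjustment and from targeting 6 months. This stands.
- Silence on sphericity is not a statement that no correction will be made, and such corrections are routine in software. This stands, so the 6-8% is conditional.
- Section 8.3 already plans a conditional weight gain analysis for 1-6 months, which conditions 6-month weight on 1-month weight. A 1-month-adjusted 6-month comparison therefore exists for weight, though not for the growth-trajectory measure.
- A reader might infer that the follow-on trial will be missized. The documents do not say that this model's estimate will be the planning effect, so the factor of 1.78 is only a what-if.
- It is too strong to say that no difference at 1 month is possible. Randomization comes first, and the documents do not say whether parents know the allocation by then. What can be said is that no intervention component has yet been delivered.

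None of this supplies a named test or a single effect estimate.

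**Conclusion.** The point holds in this form: the 1-6 month model uses a pre-intervention value as an outcome level, makes no baseline adjustment, and leaves the test of the intervention unnamed.

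The factor of 3/4 is exact for the group main effect over the four common visits, and applies only if that term is reported. The interaction is not diluted, but with 3 df it gives no single estimate. In the assumed scenario its corrected power falls about 10-20 points short of the adjusted 6-month difference. That margin depends on the assumed correlation and effect shape, and it can vanish, for example with equal correlations of 0.8 and a constant effect.

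The primary endpoint does not use this model, and the sample size rests on feasibility with no power claim. All power figures are illustrative. The change is worth making because it is cheap, not because the trial depends on it.

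**What to change.** Rewrite the growth sentence in section 8.3 so that:

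1. the 1-month value is a covariate;
2. the outcomes are the 2-, 4- and 6-month values, modelled with visit, group and group-by-visit;
3. the covariance is unstructured, or a sphericity correction is stated;
4. the adjusted group difference at 6 months, with its confidence interval, is named as the reported estimate.

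Keeping the 1-month level and prespecifying the group contrast in change from 1 month would also be acceptable, though less efficient.

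The cost is one sentence and no new data. There are two downsides. Infants with only a 1-month value contribute no response, though they carry no information on the later effect. The covariate is measured after randomization, so the text should state that it precedes delivery of every intervention component.

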informed of the volume to expect at the subsequent visit in one month should the child maintain the same weight-for-age percentile, again with a 10% reduction.

10% was chosen for this pilot because it balances feasibility (relatively likely that parents can comply) and safety (unlikely to cause failure-to-thrive by reducing total daily formula volume by ~3 ounces)

6. Parents will be given instruction to prepare the formula volume in each bottle on the lower end of what they anticipate the infant will eat. For example, if they anticipate the infant will consume 3-4 ounces per feed, they will prepare 3 ounces at first. If hunger cues persist, they will then prepare an additional 1-2 ounces of formula.

7.2.3 Visit 3

Age 2 Month Visit (42-77 days)

Both study groups:

1. Anthropometrics of infant (weight, recumbent length)
2. Diary cards to be completed for the 3 days following the visit
3. Diary cards to be completed x 3 days prior to next study visit

Intervention group only:

1. Recommend formula volumes for the next month based on Visit 2 procedures
2. **If, for a second consecutive month, the child has WFL \geq 75th percentile on the WHO WFL growth chart**, recommended daily formula volumes will be calculated based upon the child's current age, weight, and energy requirement (kcal/kg/day) with a 15% reduction in daily volume. Further, parents will be informed of the volume to expect at the subsequent visit in one month should the child maintain the same weight-for-age percentile, again with a 15% reduction.

7.2.4 Visit 4

Age 3 Month Visit (78-109 days): Intervention group only

1. Anthropometrics of infant (weight, recumbent length)
2. Diary cards to be completed for the 3 days following the visit
3. Diary cards to be completed x 3 days prior to next study visit
4. Recommend formula volumes for the next month based on Visit 2 and 3 procedures

7.2.5 Visit 5

Age 4 Month Visit (110-140 days)

Both study groups:

1. Anthropometrics of infant (weight, recumbent length)
2. Diary cards to be completed for the 3 days following the visit
3. Diary cards to be completed x 3 days prior to next study visit

Intervention group only:

4. Recommend formula volumes for the next month based on Visit 2 and 3 procedures

5. Provide handouts on soothing fussy infants, feeding

7.2.6 Visit 6

Age 5 Month Visit (141-171 days) – Intervention Group Only

1. Anthropometrics of infant (weight, recumbent length)

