8.0 Number of Subjects and Statistical Plan

8.1 Number of Subjects

Indicate the maximum number of subjects to be accrued/enrolled. Distinguish between the number of subjects who are expected to be enrolled and screened, and the number of subjects needed to complete the research procedures if applicable (i.e., numbers of subjects excluding screen failures.)

For this pilot study, 60 infants will be recruited. We believe that this number of infants who meet the inclusion/exclusion criteria can feasibly be recruited over a 6 month period.

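### Section 8.3 names no covariance structure or sphericity correction for the 1–6 month growth analysis; if run uncorrected, its group-by-visit test would be modestly anti-conservative

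*Combined protocol and SAP*

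**What the plan says.** Section 1.3 lists growth trajectory over ages 1–6 months among the secondary endpoints. Section 8.3 gives its analysis in one sentence: "we will fit a repeated measures ANOVA of BMI, with visit and study group as within and between factors, respectively". That sentence does not say whether the univariate or the multivariate test will be reported, whether an epsilon correction applies, what within-infant covariance is assumed, or which term (group or group-by-visit) answers the question. No significance level is stated.

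The design facts that matter here are in Sections 7.1 and 8.1. On the control arm, Section 7.1 says "Control infants will follow the same procedures, but will not have scheduled visits at ages 3 and 5 months", and that "their visits will correspond to usual care well child visits at ages 1, 2, 4, and 6 months". The visits at which the arms can be compared are therefore 1, 2, 4 and 6 months. On size, Section 8.1 says "For this pilot study, 60 infants will be recruited", and Section 8.2 bases that number on feasibility, with no power calculation, SD or correlation.

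**The concern.** A difference between arms in trajectory is tested by the group-by-visit term. In a within/between ANOVA, the univariate F test of that term has its nominal error rate only under sphericity, meaning that the difference between any two visits has the same between-infant variance. Infant growth data are unlikely to satisfy this. Two measurements a month apart are more alike than two measurements five months apart, and infants who gain persistently faster or slower spread out with age. Without a correction, the F test then refers to too many degrees of freedom and the p-value comes out somewhat too small.

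What is at stake is one secondary claim, that the arms followed different growth paths. There is also a pre-specification issue: with nothing named, the uncorrected, corrected and multivariate p-values would all be available once the data are seen.

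**Working it through.** **No figure to reproduce.** The documents state no alpha, SD, within-infant correlation or error rate for this test. The check is a simulation under no true effect, over a range of assumed covariances.

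**Inputs**
- From the documents: 60 infants (8.1); shared visits at 1, 2, 4 and 6 months, so k = 4 (7.1).
- Assumed: 1:1 allocation (30 per arm), normal data, equal covariance in both arms, nominal two-sided 5%.

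**Why sphericity fails under decaying correlation.** With unit variance and correlation ρ per month, the difference between two visits d months apart has variance 2(1 − ρ^d). For ρ = 0.8:
- months 1 to 2 (d = 1): 2(1 − 0.8) = 0.40
- months 2 to 4, and 4 to 6 (d = 2): 2(1 − 0.64) = 0.72
- months 1 to 6 (d = 5): 2(1 − 0.328) = 1.34

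Sphericity would need these to be equal.

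**Degree of departure.** Box's epsilon is ε = tr(A)² / [(k − 1) tr(A²)], where A is the visit covariance matrix centred by rows and columns. For ρ = 0.8, tr(A) = 1.335 and tr(A²) = 0.826, so ε = 1.783 / (3 × 0.826) = 0.72. Sphericity is ε = 1; the lowest possible value for k = 4 is 1/3.

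**Simulated type I error.** The uncorrected F test has k − 1 = 3 and (60 − 2) × 3 = 174 degrees of freedom. There were 40,000 trials per row, so the Monte Carlo standard error is about 0.1 point.

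| Assumed covariance | ε | Uncorrected | Greenhouse-Geisser |
|---|---|---|---|
| Compound symmetry | 1.00 | 4.9% | 4.5% |
| ρ = 0.5 per month | 0.89 | 5.6% | 4.7% |
| ρ = 0.7 | 0.78 | 6.3% | 4.7% |
| ρ = 0.8 | 0.72 | 6.8% | 4.9% |
| ρ = 0.9 | 0.66 | 7.0% | 4.8% |
| ρ = 0.95 | 0.63 | 7.2% | 4.7% |
| ρ = 0.8, SD rising 1 to 1.5 | 0.68 | 7.1% | 4.9% |
| ρ = 0.9, SD rising 1 to 1.5 | 0.61 | 7.5% | 4.9% |
| Random intercept and slope, moderate slope | 0.82 | 6.2% | 4.9% |
| Random intercept and slope, strong slope | 0.53 | 8.4% | 5.0% |

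A second simulation over similar structures gave about 5.3–7.3% uncorrected, 5.1% under compound symmetry and 4.5–4.9% with Greenhouse-Geisser. Together the non-spherical structures span about 5.3–8.4%.

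**Ceiling.** At ε = 1/3 the statistic behaves as F(1, 58) but is compared with the 5% critical value of F(3, 174), which is 2.66. P(F(1, 58) > 2.66) = 10.9%.

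**Is spacing the cause?** Four equally spaced monthly visits give 6.9% (ρ = 0.9) and 6.5% (ρ = 0.8), against 7.0% and 6.8% at 1, 2, 4 and 6 months. Spacing adds at most about 0.3 point.

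**Other checks**
- The group main effect stays at 4.9–5.1% throughout.
- Fewer completers change little: at ρ = 0.8, 6.5% with 24 per arm and 6.7% with 20.
- In the non-spherical rows, the Huynh-Feldt correction gives 4.9–5.2% and the multivariate test, which leaves the covariance unstructured, 4.8–5.1%.

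**The case against.** The strongest reply is that Section 8.3 never says the test will be uncorrected. A repeated measures ANOVA can be reported with an epsilon correction or as a multivariate test, and either holds the error near 5%. That stands: the defect is under-specification, and the inflation is conditional on no correction being used. It does not dispose of the point, because nothing in the documents commits the sponsor to a correction, and the within/between wording most naturally describes the univariate test.

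The size can also be challenged. It rests entirely on assumed covariances; with faster decay it shrinks (5.6% at ρ = 0.5), and in absolute terms the excess is about 0.3 to 3.4 percentage points. That stands too.

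A reader might go further and infer that the irregular visit schedule makes the assumption fail by design. The comparison with equally spaced visits does not support this; fading correlation and growing variance drive the effect.

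A reader might also infer that the next trial would be wrongly sized, since Section 8.2 says the pilot data will be used for that. Sample-size planning uses estimates of differences and variances, and non-sphericity alters the reference distribution of an F test without biasing visit-specific group differences. That inference is not supported.

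Finally, the same sentence raises other questions: it models BMI where Section 1.3 specifies weight-for-length, and controls have no 3- or 5-month visits. Those are separate. Settling the index and the visits would not by itself settle the covariance.

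**Conclusion.** The point holds in a limited, conditional form. Section 8.3 leaves the covariance structure and any sphericity correction unspecified for a listed secondary endpoint. Run uncorrected, the group-by-visit test would have a type I error of about 5.3–8.4% at a nominal 5% over the structures tried, and at most about 10.9%. These figures assume 30 per arm, normal data, equal covariance in both arms and a two-sided 5% level; the documents supply nothing to narrow the range.

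The documents do not support saying that the planned p-value is too small as a matter of fact, because they do not say how the test will be run. The group main effect and the primary endpoint (conditional weight gain from birth to 6 months) are not affected. For a feasibility-sized pilot this is a cheap improvement to the plan, not a flaw that threatens its main result.

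**What to change.** In Section 8.3, replace the repeated measures ANOVA with a linear mixed model for repeated measures at the visits common to both arms (1, 2, 4 and 6 months): visit, group and group-by-visit as fixed effects, an unstructured within-infant covariance, and Kenward-Roger degrees of freedom. Name group-by-visit as the test of a trajectory difference. The covariance must be stated, because a mixed model with only a random intercept imposes compound symmetry and would leave the problem in place. The model also keeps the available measurements of infants who miss a visit or are withdrawn, whom a complete-case ANOVA would drop.

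If the ANOVA is kept, state that the group-by-visit test uses the Greenhouse-Geisser correction. That restores an error of about 4.5–5.0% in the simulations.

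The cost is about one sentence, with standard software and the same data. The downside is slightly fewer effective degrees of freedom and a marginally less favourable p-value.
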